### **Ecological Momentary Assessment**

Participants will monitor smoking for a total of three weeks: the first week of treatment, the first week of the quit attempt, and the first week following the end of treatment. Participants will be paid \$25 per week for monitoring. Participants will also have the opportunity to earn an extra \$25 per week in incentive pay for returning fully completed electronic diaries. During the monitoring period, participants will record any smoking lapses on the electronic diary (ED), immediately after smoking. Smoking lapse assessments will be accompanied by a "situational assessment" including situation,

activity, smoking craving, mood, and PTSD symptoms. In addition, participants will complete situational assessments on at least five occasions per day selected at random by the ED. Random occasion assessments will be stratified every 2.5 hours. The timing of these assessments will be random with the constraint that no prompts will be given for 10 minutes after a cigarette entry.

Prompting will cover all waking hours. When the diary is not completed, up to 3 reminder signals will be emitted at 1-minute intervals and then the diary program will become inaccessible until the next scheduled occurrence. Smokers will be instructed to stop what they are doing when they hear the signal or plan to smoke a cigarette and complete a diary record, which will take about 1 minute. They will be told to ignore any signal that occurs during an incompatible activity (e.g., driving). To increase adherence, participants will be allowed to suspend prompting when responding would be too costly (e.g., church, driving). In previous research using similar methodology, participants suspended prompting only 2 times per week. Additionally, participants will be able to delay an assessment with a 5-minute delay function. Daily start and stop times will be programmed individually according to each participant's usual sleep pattern and entries will be time-stamped.

At the end of each weekly period of monitoring, participants will be asked to bring their assigned EMA device (see below for device description) to the laboratory. The study coordinator will upload all diary information onto secured server space owned by Duke University Medical Center (B: [name] Research Lab). This server is located in Duke University Medical Center's main campus, and is only accessible to staff members with especially approved access (i.e., only staff members on [name] team). Data will be uploaded to the Duke server because Duke has an Entryware license, whereas the VA does not. Although the drive itself is within Duke's PHI zone, data being uploaded onto this server contains neither any of the 18 types of PHI nor any other types of PII. Only [name] and her study staff have access to this secured server space, which is encrypted at rest.

# Electronic Diary System Hardware and Software

The electronic diary (ED) system will be implemented on PalmOne Treo 650 handheld computers (PalmOne, Inc.), with a 4 line, 20-character per line bright CSTN backlit color display. The computer contains a 144 MHz processor with 32 megabytes of memory. It is 4.4 in. X 2.4 in. x .9 in., weighs 5.9 ounces, and is powered by a rechargeable lithium ion battery. All other computer functions will be locked out. Customized programming has been developed specifically for this project using Entryware software (Techneos Systems, Inc., Vancouver, Canada). All assessment data will be collected by means of structured input. This electronic diary procedure ensures total confidentiality, even if a palmtop is misplaced. It also ensures temporal accuracy because participants cannot delay or clump their entries. The proposed electronic diary procedure is consistent with state of the art methodology for collecting ambulatory data assessing smoking and smoking lapse.

## **Electronic Diary Training**

Several steps will be taken to train participants to use the electronic diaries (ED). Participants will be introduced to the handheld computers at session 2, watch a 20-minute instructional video, and be given an instruction manual that details the procedure and reviews specific items and decision rules. Participants will practice diary entries during the session and receive immediate feedback regarding their data. Participants will be given the Medical Center toll-free number and appropriate extension and will be encouraged to call at any time with questions or problems. Data will be downloaded at each laboratory visit. Our pilot data and data collected during the current merit review period suggest that this procedure is highly effective in producing high participant compliance.

### Risks and Data Security

Subjects' identifying information will only be available to [name] and her research staff. Data that links participants to information collected in the course of a given study will be kept separately from identifying information. This includes elements of dates, including dates of sessions. All study data will be kept in a secured file to which only study investigators will have access, S:\Nicotine Research\Study Information\Study Databases. Hard copy paper records will be stored in a locked filing cabinet in the study coordinator's locked office, within this research lab at the Durham Veterans Affairs Medical Center (DVAMC). Information from the interview and/or the questionnaires may be entered into a computerized database. This database will be stored on a VA secured computer server that is password-protected, and only accessible by [name] and study staff. If data analysis software is not available locally, a de-identified dataset will be sent to VINCI for analysis using VA-owned data analysis software (SAS). Access to data will be limited to a small number of project staff who have been trained to preserve participant confidentiality. The key linking code numbers and identifying information will be kept in a locked office in the Durham VA, and will be maintained on password-protected computers behind the VA firewall on the VA secured server (S:\Nicotine Research\Study Information\Study Logbooks). Currently, VA records control requirements dictate that all research data, including keys for identifying data, are not destroyed. All data will be stored in accordance with this policy. For study personnel who leave the research team, removal of access to research study data will be accomplished immediately. Any information security or privacy incidents will be reported to the facility's PO and ISO immediately.

To protect against potential side effects of medications used as part of this study, patients' physicians will be consulted to determine appropriateness for this trial if any potential contraindications to these medications are reported during the screening visit. In order to monitor possible side effects associated with NRT, participants will be instructed to report any side effects as soon as possible to research staff. At each session following initiation of the nicotine replacement therapy, participants will also be questioned about any side effects to further monitor any adverse reactions. All adverse

events will be closely monitored by the PI, [name], and the designated medical monitor ([name]). [name] will evaluate patient reports of adverse events to determine whether they are study related. Serious adverse events will be promptly reported to the VA Institutional Review Boards as required. Potential risks will be minimized by carefully screening participants according to the inclusion/exclusion criteria, closely monitoring symptom levels, and following established laboratory procedures.

Safety monitoring for adverse events (AEs) will be conducted in real time by [name], his primary mentor, [name], and the project coordinator. All adverse events will be indicated on the source documentation for the study, and on the specific adverse event report form (required by the Durham VAMC IRB). The following information about adverse events will be collected: 1) the onset and resolution of the AE, 2) an assessment of the severity or intensity (use existing grading scales whenever possible), 3) an assessment of the relationship of the event to the study (definitely, probably, possibly or not related), and 4) action taken (e.g., none, referral to physician, start or increase concomitant medication). The PI will determine the severity of the event, will assign attribution to the event, and will monitor the event until its resolution.

All serious adverse events (SAEs) will be reported to the DSMB and the Durham VAMC IRB within 24 hours of the investigative team learning about them. The initial report will be conducted by phone, email or fax. This initial contact will later be followed by a written report to the IRB (using their SAE reporting form).

#### Intervention Protocol

If screened potential participants are deemed eligible to participate in the study, participants will be randomized to participate in either a 12-session CPT-C with concurrent smoking cessation treatment or a smoking cessation treatment including 6 individual smoking counseling sessions, to be followed (if desired) by CPT-C six months after the quit date. Both arms of the study will include text messaging to support the quit attempt (smokefree VET), pharmacotherapy for smoking cessation, and brief monthly follow-up phone contacts by therapists to support the quit attempt. The complete randomization sequence will be generated a priori and performed centrally by the study staff.

Although participants will attend a total of 15 sessions for this study, not all study sessions will include therapy. In the CPT-C and smoking condition, participants will receive 12 sessions of combined PTSD and smoking therapy. The first 50 minutes of each session will be devoted to the randomized therapy and the last 25 minutes will be devoted to the manualized integrated smoking cessation treatment by McFall and Saxon (McFall & Saxon, 2005). Sessions 7 through 12 of the treatment sessions will include 50 minutes of the randomized therapy, and brief (five to ten minutes) check-in regarding smoking relapse prevention and/or renewed quit attempts. In the smoking cessation without concurrent CPT-C condition, there will still be 15 total study sessions, with 6

including therapy for smoking cessation and lasting 25 minutes. If, during the course of treatment, a participant is lost to contact, the study coordinator will send an IRB-approved "no-contact letter" to increase the likelihood that we re-establish contact.

It should be noted that per the study protocol, the smoking quit date is scheduled to occur on Session 7 of the study; however, we have found that participants sometimes wish to quit smoking earlier than is called for in the study protocol. The treatment manual, which was not designed specifically for this study, indicates that changing the quit date to occur earlier is reasonable if it's based on participant preferences. Per [name], a national VA expert in integrated smoking cessation, it is reasonable in cases in which, after strong recommendations from the therapist to stick to the recommended quit date, the participant still wishes to quit earlier than recommended to allow them to, and to make modifications to the skills acquisitions components of treatment (in accordance with the manual) and change medications to coincide with the participant's preferred quit date.

If a participant is randomized to receive CPT-C, consistent with the CPT-C protocol, smokers will focus on the cognitive processing treatment components. These sessions include writing a trauma impact statement, followed by the identification of "stuck points", problematic beliefs that are believed to interfere with recovery from PTSD. In addition, patients will complete A-B-C (Activating Event, Belief, Consequence) worksheets and Challenging Questions worksheets.

Therapists who are not experienced in providing the CPT-C intervention will be allowed to attend a CPT training workshop. For each therapist, he/she will be asked to provide CPT (after training) to two participants, and the therapist's fidelity ratings will be closely reviewed (see paragraph below). Eligible therapists may elect to participate in the CPT certification process, which requires ongoing consultation telephone calls provided by certified CPT trainers within VA, and administration of both CPT and CPT-C versions of the therapy (between which the only difference is the trauma account present in CPT). Consistent with recommendations in the CPT treatment manual, standard training and clinical practice of CPT in VA is for therapists to learn both forms of the treatment (CPT with written trauma account and CPT-C with more time devoted to cognitive restructuring). Because certification of therapists is important to the quality of the therapy provided in this project, therapists choosing to undergo certification processes will be encouraged to do so. In order to facilitate certification, any therapist who is beginning the certification credentialing will be allowed to provide CPT (not CPT-C) treatment for one of his/her first two assigned therapy cases.

To ensure that PTSD symptom assessments and treatment components are consistently implemented, all CAPS interviews and treatment sessions will be videotaped using digital videotaping equipment for participants who provide consent on VA Form 10-3203. A Sony Handycam DCR-SR80 will be used to collect the videorecordings. Because the Handycam has a miniUSB to USB connector, and VA computers do not allow use of

USB drives for data transfer (unless encrypted flash drives are used), the video recordings will be moved temporarily to a stand-alone computer that is not connected to any networks and does not have Internet capability. From this stand-alone computer, the recordings will be transferred to a VA computer using an IronKey encrypted flash drive issued to a study staff member. After transfer, existing copies of data will be immediately removed from the stand-alone computer, the Handycam (using instructions in the User Manual for deletion of movies), and the IronKey device. A fidelity checklist covering CPT-C has been developed in conjunction with treatment mentor [name]. Twenty percent of videotapes will be randomly selected to be reviewed by an onsite mental health professional who has had formalized training in CPT provision. The reviewer will provide feedback to the PI. In addition, recordings will be rated for CPT treatment adherence using an adherence checklist constructed with input from treatment consultants. This treatment adherence checklist will be retained as part of the treatment manual to assist in ensuring treatment fidelity during dissemination. These video recordings will be randomly chosen with the same ratios. Because the Integrated Smoking Cessation protocol is flexible and readily adapted to fit the participants' needs, ratings of fidelity to the manual would not be useful. For this reason, we will plan only to rate the fidelity of the CPT interventions. All video collected in this manner during this study will be stored electronically on the VA-secured server in a folder to which only the study staff have access (path:

S:\\VHADURMUL23\Groups1\Research\[name] CPT\Videorecordings OR S:\Nicotine Research\Study Information\Study Logbooks\CPT\Temp. Moved). After study videos have been reviewed for fidelity, or if the storage folders listed above are full, approved study staff members will move videorecordings to DVDs that are encrypted using Symantec Endpoint Encryption. Encrypted DVDs will be stored in a locked filing cabinet in a locked office suite in Bldg 1, C10006.\_All video recordings will be kept indefinitely as is consistent with VA records control policy.

## Text Messaging to Support Smoking Cessation

As part of both interventions, participants will be invited to utilize SmokefreeVET, a mobile text messaging service for military Veterans trying to quit smoking.

SmokefreeVET was developed by a joint effort of the National Cancer Institute and the U.S. Department of Veterans Affairs. The program was created to provide 24/7 encouragement, advice, and tips to help smokers quit smoking and stay quit. It is a 6 to 8 week program, depending on when you set your quit date. Users will receive 1-5 messages per day and can receive additional quit support at critical points in the quit process by using one of SmokefreeVET's keywords (URGE, STRESS, or SMOKED). Participants can opt out of supportive text messaging at any time by sending the keyword STOP. Consistent with the structure of SmokefreeVET, participants interested in utilizing it will be assisted in signing up for the program within two weeks before their planned quit date. Participants will not be required to use the texting program. If a participant prefers to use his/her own text-capable telephone to receive these texts, then he or she will be allowed to do so. However, any participant who does not have a text-capable telephone or would prefer not to use his/her own phone will be loaned an

inexpensive telephone (Samsung Gusto 2).. Participants will be informed that there may be an added privacy benefit to using the loaned phones, as any text messages would not be received on a personal phone line, and would not be associated with any personal identifying information. Any participant who chooses to use the loaned telephone will be allowed to use it for the entire treatment period. SmokefreeVET is an (up to) eightweek program, so all participants will have equal opportunity to use the texting program in its entirety. As is true with the PDA device loaned for collection of EMA data, the telephone will not contain any identifying information, and will not even contain any key connecting the device with a participant. Rather, we will track which participant has which telephone by an electronic log connecting serial number to study ID number. This electronic log is kept on a VA secured server at S:\Nicotine Research\Study Information\Study Databases.

Text messaging is a very accessible technology for phone-based health interventions, with an estimated 56% of American adults owning a smart phone (Center, 2013). In addition, data from 2010 indicate that one in six people were using their mobile phone for health-related topics (Fox, 2010). As a push technology that requires very little effort on the part of the patient, text messaging can be very useful for reminding patients of their health goals, providing timely education and coping responses, and accessing customized feedback. Preliminary research on text messaging to assist smoking cessation suggests that it is useful (Haug, 2009).

### Assessments After Screening

Prior to each session, participants will complete questionnaires to assess psychiatric symptoms and smoking variables. These include the PTSD checklist (PCL), questions about smoking behavior in the past week, and the Beck Depression Inventory (BDI-II). In the final two sessions, participants will also complete the ASI, QOLI, TRGI, PSQI-A, CAPS, treatment satisfaction, Cook Medley Hostility Scale, e-cigarette use measure, and a question about current non-study psychotherapy. In session 8, participants will complete measures of treatment credibility and expectancy using the Reaction to Treatment Questionnaire (Borkovec & Nau, 1972). At the beginning and end of treatment, therapists will rate their level of allegiance to the therapy they are using with a single question asking "Which treatment do you think leads to better outcomes?" In the final treatment session, participants will also complete measures of SmokeFreeVet usability, and the nicotine dependence stages of change measure. In session 14 (after the final treatment session), participants will be interviewed with the CAPS.

Abstinence and relapse will be monitored by ED entries and at visits 7-14. Participants will provide breath samples for carbon monoxide (CO) analysis at every laboratory visit following their quit date. The first verification of smoking abstinence will occur on the morning following their quit date. Smoking abstinence will be obtained by self-report and verified by comparing CO levels to the level obtained at the baseline visit. The chart below lists the sliding scale of CO values that will be considered validating. At the six month follow-up visit, salivary cotinine will also be used to confirm self-reported

smoking abstinence. The formula in Table 1 below uses the participant's CO reading at the screening visit to determine the threshold that will be considered as confirming smoking abstinence after the quit date for each participant.

Table 1. Carbon Monoxide Thresholds for Validating Smoking Abstinence			
CO SCREENING	AM CO LIMIT		
		AM CO Limit after Overnight	
14-15	15	Abstinence	
16-18	16	AM CO Limit Formula: [14 + (.25 *	
19-21	17	(1.33 * (SCREENCO -14)))]	
22-24	18		
25-27	19		
28-30	20		
31-33	21		
34-36	22		
37-39	23		
40-42	24		
43-45	25		
46-48	26		
49-51	27		
52-54	28		
55-57	29		
58-60	30		
61-63	31		
64-66	32		
67	33		

After saliva samples are returned to the research laboratory, they will be sent for analysis to the University of California at San Francisco Pharmacology Laboratory for analysis. Should this laboratory discontinue salivary assay analysis, or should the PI determine use of another lab is warranted for this purpose, another lab will be identified to provide this service and this new lab will be reported to the IRB. Coded samples will be sent by trained study team members in accordance with the standards of practice outlined in Research Transporting and Shipping Biological Specimens, SRS SOP 202. Saliva samples will be analyzed for the presence of cotinine using a standard cut point off 10 ng/ml to determine abstinence. A blind sample of 5% will be run again to assure test accuracy of saliva samples. Secondary smoking outcomes will include 7-and 30-day point prevalence abstinence at each assessment, where abstinence is defined as no tobacco use in the prior 7 or 30 days respectively (McFall et al., 2010)

Any participant who is unable to remain abstinent from smoking after their quit date will be encouraged to make additional quit attempts. Participants will be allowed to make as many quit attempts as necessary during their study enrollment until they are successful or until they have completed their study enrollment. There will be no additional sessions provided for those participants who do not remain abstinent.

Consistent with guidelines for Integrated Care for Smoking Cessation, participants will continue to receive brief care for smoking cessation for as long as they remain in therapy for PTSD. In the CPT-C and smoking condition, this means that study session 8 will be the first session of smoking cessation counseling that will focus on relapse prevention and encouraging those who have relapsed to make an additional attempt to stop smoking. In sessions 8-13, participants will complete questionnaires to assess psychiatric symptoms and smoking variables and continue to receive smoking cessation follow-up counseling. In the smoking cessation condition, participants will complete the six sessions included in the Integrated Care for Smoking Cessation manual, as well as completing brief smoking counseling when completing assessments at study sessions following the quit attempt.

The smoking cessation intervention is based on the research and publication efforts of [name]., and [name]. It includes assessment of smoking history and motivation for smoking cessation, pharmacotherapy, setting a quit date, stress management techniques, and behavioral strategies to use on the quit date.

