As recommended by Dillman, Smith, and Christian (Dillman, Smyth, & Christian, 2009), we will recruit participants by sending a series of four letters to those veterans who are smokers with PTSD who are registered at the Durham VA Medical Center. Based on social exchange theory, Dillman and colleagues recommend that the second letter be sent with a small token of appreciation. This token incentive serves two functions – it will encourage respondents to respond based on the principles of social exchange theory, and more importantly, it will bring additional attention to the request for participation so that it will be more readily considered. As recommended, letter two will be sent with a small selection (i.e., monetary value less than \$2) of commemorative stamps. After participants have received the second letter describing the study in detail, a study coordinator may contact them about participation. This information is included in letter 2. Only veterans who are identified via the VA's Fileman system or the MIRECC repository will be sent letters described above. Study staff members will perform random spot-checks of names and addresses on 50% of all letters prior to mailing. This will capture any sorting error that may have occurred during the preparatory procedures. Any person who contacts the study coordinator for more information about the study (whether it be through flyers, word of mouth, etc.) will be informed about the study using the IRB-approved telephone screen script. Participants who drop out will receive partial reimbursement for the time they donate. Participants will be paid up to \$545 for their complete participation. Study costs will be paid using funds from [name] Sciences Research & Development (CSR&D) Career Development Award. Screening is completed following the endorsement of informed consent and HIPAA form by the participant.

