### **Procedures**

Participants will be recruited to participate in an intervention consisting of the smoking cessation + CPT-C or smoking cessation without concurrent CPT-C. Potential participants will complete a phone screen with study personnel to rule out those who are likely ineligible. Participants will be asked to attend a total of 15 study sessions, including a screening session, counseling and/or assessment sessions (a total of 12 counseling sessions and a 1-week post-treatment follow-up in each condition), and a 6 month follow-up to verify smoking abstinence and complete assessments.

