# **Data Analysis and Hypotheses:**

The following variables will be described for the sample as a whole: minority status, marital status, age, trauma exposure, negative affect level, PTSD symptom severity, nicotine dependence, mean pack years, nicotine cigarette brand, and mean number of cigarettes smoked daily.

Because one of the aims of this study is to assess the efficacy of the combined CPT-C and smoking intervention on smoking cessation, we will analyze these variables to determine whether they change over time.

- Compared to the smoking cessation alone protocol, the smoking cessation + concurrent CPT-C protocol will result in reduced frequency and intensity of PTSD symptoms.
- Compared to the smoking cessation alone protocol, the smoking cessation + concurrent CPT-C protocol will result in reduced depressive symptoms.
- 3) The smoking cessation + concurrent CPT-C protocol will result in decreased smoking rates, relative to published data on VA smoking cessation usual care.
- 4) Greater PTSD symptom reduction during the smoking cessation + concurrent CPT-C treatment will result in longer duration to smoking lapse and relapse.
- 5) Exploratory research question: Will use of automated text messaging as an adjunct to smoking cessation be feasible, and will it impact quit rates and symptom severity?

Hypothesis 1. Compared to the PTSD Coach and smoking cessation protocol, the CPT-C and smoking cessation protocol will result in reduced frequency and intensity of PTSD symptoms. The change in PTSD symptoms over time will be analyzed using repeated-measures ANOVA, utilizing data provided at baseline, post-treatment, and 6-months post-quit. We will evaluate the potential influence of several potential psychosocial covariates on smoking abstinence, including: 1) demographics (age, race, socioeconomic

status), 2) psychiatric variables (PTSD symptom severity, depression, substance abuse/dependence), 3) smoking variables (self-efficacy, motivation to quit, social support, smokers in social group), and 4) treatment process variables (therapeutic alliance, satisfaction with treatment, attendance at sessions, homework adherence).

Hypothesis 2. Compared to the PTSD Coach and smoking cessation protocol, the CPT-C and smoking cessation protocol will result in reduced depressive symptoms. Analysis procedures for Hypothesis 2 will be the same as those used for Hypothesis 1.

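### The H1 and H2 outcome visits are timed by treatment progress, and the plan makes no provision to assess participants who stop early, so both hypotheses risk becoming completer comparisons

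*Combined protocol and SAP*

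**What the plan says.** **Timing of the outcome visits.** Procedures describes 15 sessions, including "a total of 12 counseling sessions and a 1-week post-treatment follow-up in each condition", then a 6-month visit. On the post-treatment interview, Assessments After Screening states: "In session 14 (after the final treatment session), participants will be interviewed with the CAPS". Table 2 lists the CAPS again at session 15, timed at six months from the quit date. On that date, the Intervention Protocol says "the smoking quit date is scheduled to occur on Session 7 of the study", and it lets a participant who insists quit earlier.

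**Analysis.** For Hypothesis 1: "The change in PTSD symptoms over time will be analyzed using repeated-measures ANOVA, utilizing data provided at baseline, post-treatment, and 6-months post-quit". For Hypothesis 2: "Analysis procedures for Hypothesis 2 will be the same as those used for Hypothesis 1". The text names neither the CAPS nor the PCL as the H1 measure. It defines no analysis population and no method for missing data.

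**Interim data.** Assessments After Screening says: "Prior to each session, participants will complete questionnaires to assess psychiatric symptoms and smoking variables". These questionnaires include the PCL and the BDI-II.

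**Early stopping.** Under Recruitment: "Participants who drop out will receive partial reimbursement for the time they donate". The Intervention Protocol provides a letter for a participant who cannot be reached. The section on CPT-C after follow-up has missed appointments logged or, if they interrupt study activities, reported as deviations. The Relapse section keeps participants who resume smoking in the protocol. No corresponding sentence covers a participant who stops attending therapy.

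**The concern.** Hypotheses 1 and 2 compare randomised groups, so they need outcomes from everyone randomised, including those who stop treatment. Here the post-treatment point is defined by finishing treatment and the 6-month point by a quit date within treatment. If staff read those definitions literally, a participant who stops at session 5 has no obvious date for either visit and no instruction that brings them back. A standard repeated-measures ANOVA then omits anyone missing one of its three points.

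Stopping could plausibly differ by arm. In Table 2 most treatment sessions last 1 hr 45 min with CPT-C and 55 min without, for the same $20. If those who stay are those who improve, and more people leave one arm, the comparison of completers is biased. This is first a matter of data collection: a better model chosen later can use the interim scores, but it cannot observe outcomes after stopping that nobody collected.

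**Working it through.** **1. Is there a planning figure to reproduce?** No. Population gives 70 to be recruited, and also 120 recruited to reach at least 50 enrolled. It gives no power, effect size, SD or dropout rate. The Background calls dropout from the 12-session therapy relatively low, without a number. Everything below in steps 3 and 4 is therefore illustrative, with dropout rates, correlations, effect size and 1:1 allocation assumed.

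**2. What remains for a participant who stops early?**

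| Measure | Before stopping | Post-treatment | 6 months post-quit |
|---|---|---|---|
| CAPS | Screening only | Session 14; invitation after stopping not stated | Session 15; invitation after stopping not stated |
| PCL, BDI-II | Screening and each session attended | Not stated after stopping | Not stated after stopping |

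The interim PCL and BDI-II scores exist, but the analysis takes only the three named points.

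**3. Bias in a completer comparison with no true effect.** Let improvement be standard normal in both arms, and let the tendency to stay correlate ρ with improvement. If a share d stops, the mean improvement of those who stay is shifted by

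shift(d, ρ) = ρ × φ(z_d) / (1 − d),

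where φ is the standard normal density and z_d the d-quantile.

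- d = 10%: φ(−1.282)/0.90 = 0.1755/0.90 = 0.195
- d = 30%: φ(−0.524)/0.70 = 0.348/0.70 = 0.497
- d = 40%: φ(−0.253)/0.60 = 0.386/0.60 = 0.644

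The false difference in favour of CPT-C, in SD units, is:

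| Dropout, CPT-C vs control | ρ = 0.3 | ρ = 0.5 |
|---|---|---|
| 30% vs 30% | 0 | 0 |
| 30% vs 10% | 0.3 × (0.497 − 0.195) = 0.09 | 0.5 × 0.302 = 0.15 |
| 40% vs 10% | 0.3 × (0.644 − 0.195) = 0.13 | 0.5 × 0.449 = 0.22 |

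A simulation of 2,000,000 draws at d = 30%, ρ = 0.3 gave a shift of 0.149, as does the formula. The zero row needs equal selection as well as equal dropout: at 30% in both arms, with ρ = 0.5 under CPT-C and 0.3 in control, the difference is 0.2 × 0.497 = 0.10 SD. The sign reverses if control participants leave more often, or if those who improve are the ones who leave.

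**4. Loss of precision.** For two-sided α = 0.05 and n completers per arm, the difference detectable with 80% power is (1.96 + 0.84) × √(2/n). Power is for an assumed 0.8 SD effect.

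| Enrolled | Dropout | Completers | Detectable difference | Power |
|---|---|---|---|---|
| 50 | 0% | 50 | 0.79 SD | 81% |
| 50 | 20% | 40 | 0.89 SD | 72% |
| 50 | 40% | 30 | 1.02 SD | 59% |
| 70 | 0% | 70 | 0.67 SD | 92% |
| 70 | 20% | 56 | 0.75 SD | 85% |
| 70 | 40% | 42 | 0.86 SD | 74% |

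**5. Payment.** Table 2 and the screening payment give $50 + 13 × $20 + 3 × $50 + $35 + $50 = $545, the stated maximum. The visit pay for sessions 14 and 15, $20 + $50 = $70, is already inside it.

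**The case against.** The strongest reply is that silence is not a rule. A reader might infer that participants who stop have no outcome visit. No text says so: all participants are asked to attend 15 sessions, staff may contact them to reschedule, and both arms have brief monthly telephone contacts by therapists. The consent pages are not in the public copy and may say more. This reply stands against the categorical reading. It does not fill the gap, because none of these provisions says that assessment continues once treatment has stopped.

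A reader might also infer that someone who stops before session 7 has no quit date and so no 6-month date. The documents do not support that either: a quit date is scheduled for everyone at session 7, and the end of nicotine replacement is timed from a target quit date. What is missing is a statement that this scheduled date also governs session 15.

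Third, early stoppers do leave PCL and BDI-II scores, and H1 does not name the CAPS. That softens the loss, most clearly for depression, but supplies no value at either planned follow-up point.

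Finally, unequal dropout is inferred here from session length alone, with no retention data. Control participants wait until after session 15 for optional CPT-C, which could move their retention either way.

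**Conclusion.** The concern holds as a risk that the plan leaves open. Both follow-up points are defined by treatment progress, assessment after early stopping is not provided for, and the three-point ANOVA without a stated analysis set or missing-data method makes a completer comparison the likely default. The documents do not show that stoppers will lose their visits, nor that H1 and H2 must become completer analyses.

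The size cannot be fixed from the plan. Under the assumptions in step 3 the bias runs from zero to 0.09–0.15 SD at 30% versus 10% dropout, and to 0.13–0.22 SD at 40% versus 10%. A reader might instead be tempted to say that a dropout share d inflates the effect by 1/(1 − d), that is 1.25, 1.43 or 1.67 times at 20%, 30% or 40%. That requires no gain at all in CPT-C stoppers and no change in controls. The Background reports that, in the cited dismantling study, symptoms had fallen by the end of session six. If stoppers kept half the gain, the factor 1/(1 − d/2) would be 1.11, 1.18 or 1.25. These multipliers should not be taken as an estimate.

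The change is worth making because uncollected outcomes cannot be recovered at analysis and the remedy is cheap.

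**What to change.** Amend the protocol as follows.

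- State that stopping treatment does not end outcome assessment.
- Time the post-treatment visit by the week in which session 14 is due, counted from randomisation. Table 2 and the medication timings imply weekly sessions, which puts session 14 twelve weeks after session 2 (14 − 2). The plan should state the week.
- Time the 6-month visit from the scheduled session-7 quit date, whether or not the participant quits, quits early or leaves treatment.
- Invite every randomised participant to both visits at the Table 2 payments.
- If a visit is refused, collect at least the PCL and BDI-II by telephone, and the CAPS if possible, with the mode recorded.
- Name the analysis set as all randomised participants, and use a likelihood-based mixed model that can include the per-session PCL and BDI-II scores.

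No treatment, medication or quit-date rule changes.

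**Cost.** A protocol amendment, interview time, and up to $70 per stopper within the existing maximum. At 50 enrolled and 20% to 40% assumed dropout this is 10 to 20 people, or $700 to $1,400. Some assessments would be mixed-mode and not videotaped, which weakens the planned consistency check on the CAPS for those participants.
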